### **6.5 Assessment of Subject Compliance with Study Product Administration**

The principal investigator (or her delegate) will check the inventory against the inventory records once per month. Any deviation will be documented.

### **6.6 Concomitant Medications/Treatments**

The study will collect information on concomitant medications by patient self-report at exam and again at the final clinical examination. Of particular concern to the validity of study results will be use of fluoridated toothpaste, over the counter fluoride rinses or gels, professionally administered fluorides, antibiotics, and medications used to counter dry mouth conditions. There are no medication exclusion criteria.

### **6.7 Administration of Intervention**

Arm 1: Topical application of 38% silver diamine solution to ICDAS lesions code 3-6.  
Arm 2: Atraumatic Restoration Treatment (ART) to ICDAS lesions code 3-6, followed by topical fluoride varnish (FV) to all teeth.

### **6.8 Procedures for Training Interventionists and Monitoring Intervention Fidelity**

The study interventionists (dental hygienists) will receive didactic and clinical instruction on administration of the clinical interventions. The hygienists will undergo a two-day training and calibration exercise with extracted teeth and applying the intervention on patients. The didactic instruction will include required reading, viewing of technique videos, and laboratory and clinical practice. The supervised laboratory practice will use extracted teeth in which there are natural or instructor created cavities. The clinical application will be practiced on at least one patient.

To be certified, the study interventionist must demonstrate mastery. For ART and FV application the trainee will complete a written or oral exam on procedures (from set up to cleanup); Complete no less than 8 ART on the lab bench on extracted teeth; Complete no less than 3 ART on an older adult patient with cavities; Complete at least one FV treatment on the same patient. For SDF the trainee will complete a written or oral exam on procedures; complete at least 1 treatment on an extracted tooth; complete at least 1 treatment on an older adult patient. During the actual intervention visits to the housing facility, the study dentist will be present to supervise the hygienists to make sure that the study treatment were delivered per protocol. If there is a problem with the delivery of the treatment or adherence to protocol then the

---

interventionists will be given corrective training. *For 52 week follow-up visits, where treatment will not be delivered, the study dentist may not be present.*

## 6.9 Assessment of Subject Compliance with Study Intervention

In addition to direct supervision, the interventionist will use clinical photographs to capture random images of ART restorations. These will be reviewed on a quarterly basis by the clinical dentist supervisor/gold standard trainer and corrective training will be provided if there is a problem with clinician compliance. All deviations of protocol will be documented. The clinical dentist supervisor will observe the application of the various study materials for each of the interventionists. Corrective training will be provided if there is a problem with clinician compliance. All deviations of protocol will be documented.

---

## 6.10 Study Procedural Intervention(s) Description

There is no product masking in this study.

### Study Arm 1:

Advantage Arrest. The application procedure is below:

1. The cavity will be cleaned with a dry manual tooth brush to remove debris.
2. The area will be isolated with cotton rolls. If the lesion is at the gumline, the gingiva will be coated with a thin layer of petroleum jelly per manufacturer's instructions.
3. The single use SDF vial (Advantage Arrest, Elevate Oral Care) will be opened and the manufacturer's supplied brush will be dipped into the reservoir. The SDF will be applied with the brush until the lesion is coated fully.
4. Allow to air dry. The patient can resume normal activity with no restriction.

### Study Arm 2:

Application procedure for the atraumatic restorative treatment is as follows::

1. When the lesion is on the occlusal surface, the occlusion will be checked with blue articulating paper prior to other clinical procedures.
2. The field will be isolated with cotton rolls. Soft debris will be removed with moistened cotton pellets. Then soft demineralized tooth structure will be removed with a spoon excavator at the periphery of the lesion, where there is access. A *manual* brush and pumice will be used to remove any further loose material. The cavity will be washed well with water.
3. The cavity will be conditioned with the liquid of the glass ionomer (polyacrylic acid) for 10-15 seconds and then rinsed, maintaining moisture control throughout.

---

4. The resin reinforced glass ionomer restorative (Fuji II LC Automix, GC America) will be inserted into the cavity using the manufacturer's delivery device and then coated with Fuji Coat (GC America). The restoration will then be light cured for 20 seconds.

Following the restorative treatment, the patient will be treated with fluoride varnish, as below.

FluoriMax Varnish. By quadrant or arch, all of the teeth will be coated with fluoride varnish (FluoriMax, Elevate Oral Care) using the manufacturer's brush system. The varnish container will be shaken for a few seconds before application. A single application from posterior to anterior will be used and then the occlusal surfaces will be coated, with no reapplication. The material will be allowed to dry 3-5 seconds and the patient instructed to avoid eating or dental hygiene for 4 hours.

If a participant reports any issue with the applied treatment within one week of the treatment date, the study team will return to the housing facility to examine and correct the treated tooth as needed. Within 48 hours, the study team will call the participant to ask the participant if the issue has been resolved and will administer a paper safety questionnaire. The completed paper safety questionnaire will be stored in the CRF folder and documentation of the return visit/treatment will be added to the participant's electronic record.

## 6.11 Administration of Procedural Intervention

Arm 1(SDF): SDF will be administered by a licensed dental hygienist at the baseline visit, and the 26-week visit.

Arm 2(ART +FV): ART will be administered by a licensed dental hygienist at the baseline visit + Fluoride Varnish application at baseline and the 26-week visit. If ART requires scooping out the decay then a licensed dentist will scoop the decay and then have the hygienist complete the ART intervention. *For 52 week follow-up visits, where treatment will not be delivered, the study dentist may not be present.*

## 7 STUDY SCHEDULE

Prior to any of the following actions, facilities will be randomized into one of two treatment intervention arms.

Refer to Appendix A for the Schedule of Events.

Temporary COVID-19 pandemic procedures:

Recruitment/Enrollment

- Study staff will receive contact information from Service Coordinators/Housing Managers for those who are interested in the study.
- Study staff will contact interested individuals by phone or video-conference and send them paper consent forms. They will review the consent form with the individual by phone or video-conference and answer any questions they may have and ensure the individual understands the study and all study procedures.
- Individuals will then be asked to sign the consent form and mail it back to the study staff in a stamped, self-addressed envelope provided to them. Study staff will sign the form and send a copy of the signed form back to the individual, along with a paper copy of the surveys.
- Study staff will then contact the individual by phone or video-conference to complete the surveys. Individuals will be asked to follow along on the paper survey while study staff reads the questions to them over the phone or video conference. Participant responses will be entered into REDCap by study staff during the phone call or video-conference.
- Exam/treatment appointments will be scheduled once the housing sites, funding agencies, IRB and CWRU have approved study personnel returning to being on-site at the housing sites.

26 and 52-week Follow-Up Data Collection

- Study staff will contact individuals due for the 26 and 52-week follow-up survey, to arrange a time to complete the survey by phone. Study staff will mail the survey to the individual prior to the survey completion phone call.
- Study staff will then contact the individual by phone at the scheduled time to complete the surveys. Individuals will be asked to follow along on the paper survey while study staff reads the questions to them over the phone. Participant responses will be entered into REDCap by study staff during the phone call.
- 26-week and 52-week exam/treatment appointments will be scheduled once the housing sites, IRB and CWRU have approved study personnel returning to being on-site at the housing sites

Once the COVID-19 pandemic ends, we will follow the original proposed plan.

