### 5.3 Strategies for Recruitment and Retention

We will use prior successful strategies in recruiting and also solicit input from our stakeholders. Strategies that will be used are as follows: Service coordinators at all 22 facilities will serve as site liaisons. The study PI/project manager will provide the service coordinators with an introductory letter/flyer containing study information to be given to tenants and to be posted in public areas of the facility. Service coordinators will first arrange an informational meeting (study dentist will give a talk on the interventions as suggested by our stakeholders), and will arrange a second recruitment meeting for study staff to present information regarding the study at scheduled group events (e.g. tenant meetings, health fairs). For planning purposes, service coordinators will have a sign-up sheet for those interested in the sessions. Study staff will schedule those who are interested and meet the inclusion criteria for one-on-one sessions at the housing facility to obtain informed consent and collect baseline survey data. Baseline dental exam and treatment appointments will then be scheduled at each facility according to a designated exam day(s) for each facility, which will occur approximately 1-2 weeks following consent and baseline data collection. Six and twelve month dental exams/treatment and one-on-one interviews for follow-up survey completion for each time point will also occur at the housing facility where participants reside

Retention strategies for participants will include:

- Participants will be given promotional items (i.e. pens, magnets) with the study logo and contact phone number at recruitment.
- Alternate contact information for family/friends that may be able to reach the participant if primary contact information becomes invalid will be obtained at recruitment.
- Annual birthday/holiday cards will be sent to participants to maintain contact.
- Newsletters will be sent twice a year with updates on the study's progress (i.e. recruitment), and a reminder to update their contact information (by phone or mail).
- Assistance from service coordinators or other facility staff will also be solicited for hard to reach/contact participants.
- *Due to COVID-19 delays, an additional 4 housing sites are being added to the study to accelerate recruitment.*

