## 5.4 Treatment Assignment Procedures

### 5.4.1 Randomization Procedures (RQ-2)

Randomization is at the level of the cluster (housing facility) for logistical efficiency. This will greatly reduce the potential for error that could otherwise occur with people at the same site assigned to different treatments. Furthermore, keeping the same treatment at each site reduces chances of 'contamination' (i.e. participant discussing their treatment with others). Additionally, stratified cluster randomization will be used, i.e. a block (constrained) randomization approach in which balance over treatments is assured for 2 key cluster-level (stratification) variables, namely facility size (>100 versus ≤100 residents), and geographic location (Cuyahoga County vs other). The project statistician, [name] will generate the randomization scheme for the 22 + 4 additional housing facilities. While the randomization is at the housing level, the study objectives, interventions and primary outcomes all pertain to the individual level (RC-1).

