### 5.4.2 Masking Procedures (IR-6)

We will attempt blinding of participants to the study group, but this may not be possible due to SDF color change.

The hygienists will be unaware of the treatment assignment when they go to their respective housing facilities. For all treatment visits, assessments will be conducted prior to the intervention delivery.

Two hygienists will go to the housing facility randomized to the SDF arm and the other two will go to the ART + FV arm. The baseline treatment to be applied will be revealed only after the baseline caries exam has been completed. At the 6 month follow-up visit, the two hygienists that applied SDF will now go to the facilities randomized to the ART + FV facilities and vice-versa to conduct the 6-month follow up caries assessment exam and treatment. We will follow similarly for the 12-month follow-up visit. By this strategy, we will make sure that potential bias of the hygienist evaluating their own work is minimized. Additionally, periodically we will check for the quality of the assessment data by [name] randomly examining 20% of the participants.

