### 7.1 **Baseline Visit ( $T_0$ ) (Day -30 to 14)**

#### **Recruitment/Enrollment**

Study staff will recruit potential participants at the 22 participating housing facilities in coordination with the housing service coordinators and by using an in person approach at venues scheduled at the housing facility.

- Service coordinators will be provided with an introductory letter/flyer containing study information to be given to tenants and to be posted in public areas of the facility and will arrange an informational meeting for tenants (study dentist will give a talk on the interventions as suggested by our stakeholders).
- Service coordinators will arrange in-person recruitment meetings for study staff to present information regarding the study at scheduled group events (e.g. tenant meetings, health fairs, study informational presentations). For planning purposes, service coordinators will have a sign-up sheet for those interested in the sessions. At the conclusion of the session, study staff will meet individually with those interested to:
  - Review inclusion/exclusion criteria to determine eligibility (**Refer to Sections 5.1, 5.2**) utilizing the Screening and Eligibility Form
  - Obtain informed consent by reviewing the written consent form (Refer to Section 15.3) with the potential participant; ensuring comprehension of the study and

procedures, answering any questions, signing the consent form acknowledging that informed consent was reviewed and obtaining subject signature acknowledging consent was obtained. Consent will be obtained one time prior to the initiation of any study activities and will remain in effect for the duration of the study.

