## Follow-Up Data Collection

- Study staff will contact participants by phone (within 48 hours of treatment) to complete the safety survey.
- Study staff will interview participants one-on-one at the housing facility to update contact information and enter participant responses to the oral health symptoms, tooth pain/sensitivity, oral health quality of life, *COVID-19 dental visit* and the satisfaction survey.
- Study staff will randomly select 24-30 participants who have completed treatment for three focus group sessions to be held at a housing facility during years two, *three and four*. Participants will be selected from those who have completed treatment and is geared to understanding participant experiences with non-surgical regimens and to identify ways to improve and disseminate in other community-based settings nationally.

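### Sites are randomised before recruitment, and the plan does not keep the arm from the staff who recruit, consent and interview, or from the study dentist, leaving consent and self-reported pain open to bias of unknown size and direction

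*Combined protocol and SAP*

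**What the plan says.** **Order of events.** Section 7 opens its schedule with "Prior to any of the following actions, facilities will be randomized into one of two treatment intervention arms". Section 5.4.1 gives the unit: "Randomization is at the level of the cluster (housing facility) for logistical efficiency". Every enrolled resident of a building is therefore assigned the same treatment.

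**Before consent.** Sections 5.3 and 7.1 describe an informational meeting at which the "study dentist will give a talk on the interventions as suggested by our stakeholders". Study staff then see interested tenants individually, check eligibility, take consent and collect the baseline questionnaires. Section 5.3 puts the exam and treatment day about one to two weeks later, and Appendix A places baseline pain at week -2.

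**Masking.** Section 5.4.2 says: "The hygienists will be unaware of the treatment assignment when they go to their respective housing facilities". The treatment is disclosed to them only once the baseline caries exam is finished. Participant blinding will be attempted, with a warning that the SDF colour change may defeat it. Section 13.2.1 adds that hygienists will not see baseline results at follow-up. Section 6.10 states that the products are not masked.

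**After treatment.** Under section 6.8, "the study dentist will be present to supervise the hygienists to make sure that the study treatment were delivered per protocol". For follow-up pain, quality of life and satisfaction, sections 7.2 and 7.3 say: "Study staff will interview participants one-on-one at the housing facility". In Figure 15.3.1, study staff also enter the treatment log.

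**The concern.** In an individually randomised trial, concealment up to the moment of enrolment protects the decision to consent. Here the arm of every future participant at a site is fixed before anyone is approached. If a recruiter or the speaker at the meeting knows it, emphasis and expectations can differ by arm, and so can the kind of person who agrees. Randomising sites does not protect against this. Nor does the intention-to-treat analysis in section 11.4, because the selection occurs after randomisation and before a person enters the analysis.

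The second route is through reporting. Tooth pain is a primary outcome and is self-reported, often to a staff member. A participant's expectation, or an interviewer's knowledge of the site's treatment, can act on the answer directly. In a non-inferiority comparison, a bias that favours SDF makes a false claim easier, and a bias against SDF makes a true claim harder.

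**Working it through.** **1. Who is covered at each step**

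| Step | Who acts | Masking stated |
|---|---|---|
| Site randomised (section 7; scheme generated under 5.4.1) | Project statistician | Not applicable |
| Talk on the interventions (5.3, 7.1) | Study dentist | None |
| Eligibility check, consent, baseline pain (7.1) | Study staff | None |
| Baseline caries exam (5.4.2, 7.1) | Hygienists | Unaware until the exam is done |
| Supervision of treatment (6.8) | Study dentist | None; arm necessarily known by then |
| Pain and quality-of-life interviews (7.2, 7.3) | Study staff | None |

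The stated masking begins at the exam, which comes after consent and baseline pain. The steps on either side of it have no provision. Because one treatment serves a whole building, the arm may also become known to staff and later recruits once the first residents are treated. That is an inference, but section 5.4.1 itself recognises that participants may discuss their treatment.

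**2. How many people decide at the consent step.** Section 5 plans to approach 1368 people and screen 958, at 70% consent: 1368 × 0.70 = 957.6. About 1368 − 958 = 410 would decline. This gives the scale of the step and does not measure bias.

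**3. The plan's power for pain, reproduced.** Inputs from section 11.2: 275 per arm, 25 per site, 15% dropout, ICC 0.01, SD 25, margin 8, true difference 0, one-sided alpha 0.025.

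- Completers per arm: 275 × 0.85 = 233.75. Completers per site: 25 × 0.85 = 21.25.
- Design effect: 1 + (21.25 − 1) × 0.01 = 1.2025.
- Effective n per arm: 233.75 / 1.2025 = 194.4.
- SE of the difference: 25 × √(2/194.4) = 2.54.
- Power: Φ(8/2.54 − 1.96) = 88.4%, against 89% stated.

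At ICC 0.02 the effective n is 166.4 and power is 83.1%, against 83% stated. No sample-size figure is in dispute.

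**4. Illustration of a reporting bias.** The documents give no bias estimate, so b is assumed. With a bias of b mm favouring SDF, type I error at a true difference of 8 is Φ(b/SE − 1.96). With the same bias against SDF, power at a true difference of 0 is Φ((8 − b)/SE − 1.96).

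| Assumed b (mm) | Share of margin | Type I error, favouring SDF (ICC 0.01 / 0.02) | Power, against SDF (ICC 0.01 / 0.02) |
|---|---|---|---|
| 0 | 0% | 2.5% / 2.5% | 88.4% / 83.1% |
| 1 | 12.5% | 5.9% / 5.5% | 78.8% / 72.4% |
| 2 | 25% | 12.1% / 10.9% | 65.8% / 59.1% |
| 3 | 37.5% | 21.9% / 19.3% | 50.5% / 44.6% |

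These figures use the 100-mm scale of the power calculation. Table 8.1.1 lists other pain instruments, so they show sensitivity on the planning scale only.

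**The case against.** **Silence is not disclosure.** A reader might infer that recruiters and interviewers are told the arm, or that the dentist's talk covers only the site's own treatment. The documents do not support either. The talk is on the interventions in the plural, participant blinding is to be attempted, and the consent pages and training protocol are not available to check. What stands is that no provision withholds the arm from these people.

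**Trial entry is partly masked.** Caries eligibility is settled at the baseline exam by hygienists who do not yet have the assignment. This stands and limits the selection route. It does not reach the earlier consent or the baseline pain interview.

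**Interviewer influence may be smaller than it looks.** Section 12 has participants completing their own questionnaires, section 15.2.5 allows paper or tablet, and Figure 15.3.1 lists entry by participant and staff for Questionnaire B. Staff reading out the questions belongs to the temporary COVID-19 telephone procedure in section 7. This stands as mitigation, but sections 7.2 and 7.3 still specify one-on-one interviews in which staff enter the answers.

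**The analysis offers some protection.** Pain is analysed as change from a pre-treatment baseline, and the GEE models adjust for sociodemographic, medical and behavioural variables. Neither removes differences in unmeasured characteristics or in how pain is reported after treatment.

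**Much recruitment is past.** The version 14.0 entry in the revision history adds the sites where enrolment was completed. Concealment before consent can therefore help only further enrolment. This stands and shapes the fix.

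**Conclusion.** The point holds as a gap in the procedure. Following the stated sequence leaves consent and a self-reported primary outcome exposed to knowledge of the arm, and a simple alternative exists. It is not evidence that bias occurred.

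Size and direction are unknown. The 2-mm case (a quarter of the margin; type I error about 12%, or power about 66%) rests on an assumed shift together with the plan's SD, ICC and dropout. A reader might infer that poor masking always helps a non-inferiority claim. That does not follow. Random error in the pain score widens the interval and makes the claim harder, and expectations about staining could work against SDF. Only a systematic difference favouring SDF inflates the false-positive rate.

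The change should be made, and no sample-size figure needs altering.

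**What to change.** 1. **Any further enrolment.** Amend sections 5.4 and 7 so that the project statistician holds each site's allocation and releases it only when that site's consent and baseline questionnaires are complete. The one-to-two-week gap before the exam day allows this. Use one fixed talk and flyer that describe both treatments identically at every site.
2. **Remaining follow-up.** Have Questionnaire B (pain, quality of life) given by existing staff who were not at that site's treatment day, where rosters allow. When Questionnaire D (satisfaction) is given at the same contact, ask B first. Leave the safety questionnaires at their scheduled times: the pre-exam form and the post-treatment call have timings of their own, so moving them would conflict with sections 7.1 to 7.3 and Appendix A.
3. **Sites already recruited.** Report approached, consented and eligible numbers, and baseline pain and lesion counts, by arm and site. Section 11.4 already commits to CONSORT reporting; this adds the site-level detail needed to look for differential recruitment.

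The cost is a short amendment, later confirmation of each site's supplies and some roster arranging. Section 7 keeps on-site staff to a minimum under the COVID-19 procedures, so interviewer separation may not be possible at every visit. Where it is not, record that.
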